7.1 Intent-to-Treat (ITT) Population

The ITT population includes all randomized subjects. The primary analysis will be performed on the ITT population with the primary estimand detailed in [Section 2.6](#) of this SAP. Subjects in the ITT population will be analyzed as randomized.

7.2 Per Protocol (PP) Population

The PP population includes subjects in the ITT population who do not have significant protocol deviations. Protocol deviations will be assessed prior to database lock and unmasking. The PP population will be analyzed using observed data only for efficacy variables. Subjects in the PP population will be analyzed as treated.

7.3 Safety Population

The Safety population includes all randomized subjects who have received at least one dose of the investigational product (IP). The Safety population will be analyzed for all safety assessments. Subjects in the Safety population will be analyzed as treated.

8. General Statistical Considerations

8.1 Unit of Analysis

Safety endpoints will be analyzed for both eyes. For subject-level efficacy endpoints, the unit of analysis will be the subject. For eye-level efficacy endpoints, the unit of analysis will be the study eye as defined by the following:

Study Eye: Eyes are eligible for analysis if they meet all of the inclusion criteria. In the case that both eyes are eligible for analysis, the study eye will be the eye with worse (higher) central corneal fluorescein staining score at Day 1. If the central corneal fluorescein staining score is the equivalent in both eyes, then the right eye will be selected as the study eye.

8.2 Missing or Inconclusive Data Handling

The primary efficacy analyses will be performed using the multiple imputation methodology specified in Estimand 1. If the rate of missing data for EDS-VAS is imbalanced between treatment groups, then trimmed means methodology will be executed as specified in Estimand 2. Full descriptions of Estimands 1 and 2 are provided in [Section 2.6](#) of this SAP. Additional sensitivity and supportive analyses may be executed, including:

- Multiple imputation via placebo group-based pattern-mixture model (PMM) imputation with the ITT population under the assumption of missing not at random for all missing.
- A tipping point sensitivity analysis with corresponding imputations of increasingly more conservative “penalties” added to the active group PMM imputations, until such point that the treatment group difference is no longer significant.
- Multiple imputation via randomized treatment group-based Markov Chain Monte Carlo (MCMC) with the ITT population under the assumption of missing at random for all missing.
- Last observation carried forward (LOCF) imputation methodology using the ITT population.
- Observed data only using ITT and PP populations.

No secondary efficacy endpoints or safety endpoints will be imputed.

8.3 Definition of Baseline

Baseline measures are defined as the last measure prior to the initiation of study treatment, usually at Day 1.

8.4 Data Analysis Conventions

All data analyses will be performed after the study is completed and the database has been locked and released for unmasking. Statistical programming and analyses will be performed using SAS® Version 9.4 or higher. Output will be provided in RTF (rich text format) for tables, listings, and figures using landscape orientation. All study data will be listed by subject, treatment, and visit (as applicable) based on all enrolled subjects unless otherwise specified.

All summaries will be presented by treatment group and visit where appropriate, unless otherwise specified. Listings will be presented for all data collected on the eCRFs, sorted by subject id number and visit.

Summaries for continuous and ordinal variables will include the number of observations (n), arithmetic mean, SD, median, minimum, and maximum. Minima and maxima will be reported with the same precision as the raw values; means and medians will be presented to one additional decimal place than reported in the raw values. Standard deviations will be presented to two additional decimal places than reported in the raw values. Summaries for discrete variables will include frequency counts and percentages. All percentages will be rounded to one decimal place (i.e., XX.X%).

All statistical tests will be two-sided with a significance level of 0.05 ($\alpha = 0.05$) unless otherwise specified. Confidence intervals (CI) will be two-sided at 95% confidence levels where appropriate. All p-values will be rounded to four decimal places; p-values less than 0.0001 will be presented as "<0.0001"; p-values greater than 0.9999 will be presented as ">0.9999."

8.5 Adjustments for Multiplicity

Hierarchical fixed sequence testing will be used to maintain the type I error rate. The primary analysis will first test the difference in CFB (Day 1) of CCSS in the study eye at Day 57 in the ITT population using the primary estimand. If the test of the difference between treatment groups is statistically significant at the two-sided alpha = 0.05 level in favor of Tanfanercept, then the study will be considered a success, Tanfanercept will be declared to be superior to placebo in the change from baseline (Day 1) of CCSS at Day 57, and the difference in the change from baseline (Day 1) of EDS at Day 57 will then be tested at the two-sided alpha = 0.05 level in the ITT population.

If, in addition to a statistically significant test of the difference in change from baseline (Day 1) of CCSS in the study at Day 57 in favor of Tanfanercept, the test of the difference in the change from baseline (Day 1) of EDS at Day 57 in the ITT population with the primary estimand is also statistically significant in favor of Tanfanercept, then Tanfanercept will be declared superior to placebo in both the change from baseline (Day 1) of CCSS and the change from baseline (Day 1) of EDS at Day 57.

Secondary efficacy analyses will not be type-I error controlled and will be considered hypothesis generating.

9. Disposition

9.1 Subject Disposition

Subject disposition will be presented in terms of the numbers and percentages of subjects who completed the study and discontinued from the study. Subjects who are not discontinued from the study will be considered study completers. Disposition will be summarized by treatment group and for all subjects. The total number of screened subjects with the number and percentage of screen failure subjects will be summarized as well.

The number of randomized subjects in each analysis population (ITT, PP, and Safety) will be displayed by treatment. The ITT population uses treatment as randomized; PP and Safety populations use treatment as treated. Percentages are based on the total number of subjects randomized in each treatment group.

The number and percentage of subjects prematurely discontinued from the study and the reasons for study discontinuation will be summarized by treatment group for all randomized subjects. The reasons for study discontinuation that will be summarized include: Pregnancy, AE, Lack of Efficacy, Unmasking When Medically Necessary, Protocol Violation, Administrative Reasons (e.g., Inability to Continue, Lost to Follow Up), Study Termination by Sponsor, Subject Choice, and Other. A subject listing of disposition will be provided that includes the date of and reason for premature study discontinuation.

9.2 Protocol Deviations

The number and percentage of subjects with any, major, and minor protocol deviations will be summarized by treatment group for all randomized subjects. The number and percentage of subjects with any protocol deviation will also be summarized for the following categories: Informed Consent, Inclusion / Exclusion and Randomization, Test Article / Study Drug Instillation and Assignment at Site, Improper Protocol Procedures at Site, Site's Failure to Report Serious Adverse Event (SAE) / AE, Visit Out of Window, Subject's Non-compliance with Test Article, Subject's Use of Prohibited Concomitant Medication, Subject's Failure to Follow Instructions, and Other. A subject listing will be provided that includes the date, visit at which the deviation occurred (if applicable), deviation code, description of each deviation, whether the deviation was COVID-19 related, and the classification of whether the deviation was judged to be major or minor.

In addition, subject listings will be provided that include date of randomization, randomization number, randomization arm, actual treatment, and [REDACTED] whether inclusion and exclusion criteria were met, and inclusion in the analysis populations. A listing of subjects affected by COVID-19 discontinuations and protocol deviations will be generated as well.

A table summarizing the number of randomized subjects enrolled by site with percentages will be generated.

10. Demographic and Pretreatment Variables

10.1 Demographic Variables

The demographic variables collected in this study include age, sex, race, ethnicity, and iris color. Demographic variables will be summarized for the ITT and Safety populations separately.

Age (years) will be summarized, overall and by treatment, using continuous descriptive statistics. Age will also be categorized as follows: <65 years and ≥65 years. Age will be reported in years and calculated using the following formula:

$$\text{Age} = (\text{Informed Consent Date} - \text{Date of Birth}) / 365.25, \text{truncated as an integer}$$

The number and percentage of subjects will be presented, overall and by treatment, for age category, sex, race, ethnicity, iris color for the right eye (OD) and left eye (OS), [REDACTED]

A subject listing that includes all demographic variables will be provided.

10.2 Pretreatment Variables

Baseline disease characteristics will be summarized by treatment group using continuous descriptive statistics for central corneal staining score (CCSS), eye dryness score (EDS), total OSDI® score, unanesthetized Schirmer's test, best-corrected visual acuity (BCVA), and IOP. All summaries will be for the study eye, except for OSDI® which is a subject-level assessment. The scale for each assessment is provided in the variables' respective subsections in [Section 13.2](#) of this SAP. Baseline disease characteristics will be displayed for the ITT population.

11. Medical History and Concomitant Medications

11.1 Medical History

Medical history will be coded using Medical Dictionary for Regulatory Activities (MedDRA) Version 24.0.

Medical history will be summarized using counts and percentages and presented by treatment group at the subject and event level by System Organ Class (SOC) and Preferred Term (PT) using the ITT population. If a subject reports the same PT multiple times within the same SOC, that PT will only be reported once within that SOC. As with the PT, if a subject reports multiple conditions within the same SOC, that SOC will only be reported once. In the summaries, SOCs and PTs within an SOC are presented in ascending alphabetical order.

Listings of medical history will be generated separately for ocular and non-ocular data.

11.2 Prior and Concomitant Medications

Ocular and non-ocular prior and concomitant medications will be coded using World Health Organization Drug Dictionary (WHODrug) Global B3 (March 2021) and coded to the therapeutic drug class (Anatomical Therapeutic Chemical [ATC] 4 classification) and preferred name.

Concomitant medications are defined as those medications listed as having been taken (1) prior to initiation of randomized study drug administration (Day 1) and continuing for any period of time following the first administration of randomized study drug or (2) at any time following the first administration of randomized study drug (Day 1). Prior medications are reported medications that have been taken prior to and not on or after initiation of randomized study drug administration.

Concomitant medications will be summarized using the Safety population. Prior medications will not be included in data summaries, but will be provided on data listings. Concomitant medications will be tabulated for each treatment group and for all subjects using frequencies and percentages. Subjects may have more

than 1 medication per ATC class. At each level of subject summarization, a subject will be counted once if he/she reports 1 or more medications. Percentages will be based on the number of subjects in each treatment group. In the summaries, ATC classes and preferred names within an ATC class are ordered by descending frequency values based on all subjects.

Listings of concomitant and prior medications will be generated separately for ocular and non-ocular data.

11.3 Concomitant Procedures

Concomitant procedures will be coded using Medical Dictionary for Regulatory Activities (MedDRA) Version 24.0.

Concomitant procedures will be summarized using discrete summary statistics and presented by treatment group at the subject and event level by System Organ Class (SOC) and Preferred Term (PT) using the ITT population. If a subject reports the same PT multiple times within the same SOC, that PT will only be reported once within that SOC. As with the PT, if a subject reports multiple conditions within the same SOC, that SOC will only be reported once. In the summaries, SOCs and PTs within an SOC are presented in ascending alphabetical order.

Listings of concomitant procedures will be generated separately for ocular and non-ocular data.

12. Dosing Compliance and Treatment Exposure

12.1 Dosing Compliance

Dosing compliance will be calculated as:

$$\text{Dosing Compliance (\%)} = (\text{Number of doses taken from Day 1 to study completion/discontinuation visit} / \text{Number of expected doses from Day 1 to study completion/discontinuation visit}) * 100$$

The number of doses taken will be calculated by subtracting the number of unused vials from the number of vials dispensed plus the total number of vials missed reported in the electronic case report form (eCRF). For subjects who do not receive a dose of randomized study drug, the number of expected doses will be 0 and compliance will be defined as 0. Otherwise, the number of expected doses will be calculated as $2 \times [\text{Date of Study Completion/Discontinuation} - \text{Date of Day 1} + 1]$. If a subject discontinues on Day 1 then the number of expected doses is 1.

Dosing compliance will be summarized using continuous descriptive statistics including mean, SD, median, minimum, and maximum for the Safety Population. Additionally, a categorical summary display frequencies and percentages of those deemed compliant, under-compliant (<80%), and over-compliant (>125%).

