- Note: If only one eye qualifies then the single qualifying eye will be the study eye. In the case that both eyes are eligible for analysis, the study eye will be the eye with worse (higher) central corneal fluorescein staining at Visit 2. If the central corneal fluorescein staining is the equivalent in both eyes, then the right eye will be selected as the study eye.
- **Randomization** – subjects will be randomized according to the following two strata:
 1. Visit 2 study eye CCSS █ and
 2. Visit 1 CCSS minus Visit 2 CCSS (V1 CCSS - V2 CCSS); difference in study eye CCSS █
- **Blood Sampling** Blood samples will be collected from all subjects for immunogenicity testing █

- Study Drug Instillation at the Study Site All subjects meeting all other screening eligibility criteria after Visit 2 will be randomized to one of two treatment arms. Randomized subjects will self-administer their initial study drug dose bilaterally at the study site.
- Ora Calibra® Drop Comfort Assessments The Ora Calibra® Drop Comfort Scale will be performed immediately after instillation and then at 1, 2, and 3 minutes following instillation.
- Monitoring and Query of AEs
- Study Drug Dispensation Prior to discharge from the study site on Visit 2 (Day 1), randomized subjects will be educated in the self-administration of study drug. The initial, self-administered dose taken in-office at Visit 2 will be counted as a morning dose regardless of visit time, and subjects will be instructed to administer an evening dose that night. Subjects will receive their assigned study drug kit with sufficient supply to last until Visit 3 and will be instructed NOT to self-administer study drug on the morning of their next scheduled study visit (Visit 3, Day 8).
- Schedule Next Visit Subjects will be scheduled for Visit 3.

8.4.4 Visit 3: Day 8 ± 1 –Week 1

- Study Drug Collection All used/unused study drug vials dispensed for Days 1 to 8 should be collected and reviewed by a trained study technician.
- Site staff must confirm that subjects have NOT administered their morning study drug dose at home. If subject dosed prior to the visit, study visit procedures should begin 4 hours after time of dosing.
- Monitoring and Query AEs
- Recording of all Changes in Concomitant Medications
- Ora Calibra® Ocular Discomfort Scale
- Ora Calibra® Ocular Discomfort & 4-Symptom Questionnaire
- VAS
- OSDI[©]
- BCVA Utilizing an ETDRS Chart
- Slit-Lamp Biomicroscopy
- Conjunctival Redness
- TFBUT

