8.4.6 Visit 5: Day 29 ± 2 –Week 4

- Study Drug Collection All used/unused study drug vials dispensed for Days 15 to 29 should be collected and reviewed by a trained study technician.
- Site staff must confirm subjects have NOT administered their morning study drug dose at home. If subject dosed prior to the visit, study visit procedures should begin 4 hours after time of dosing.
- Monitoring and Query of AEs
- Record all Changes in Concomitant Medications
- Ora Calibra® Ocular Discomfort Scale
- Ora Calibra® Ocular Discomfort & 4-Symptom Questionnaire
- VAS
- OSDI[®]
- BCVA Utilizing an ETDRS Chart
- Slit-Lamp Biomicroscopy
- Conjunctival Redness
- TFBUT
- Corneal and Conjunctival Staining (fluorescein)
- Corneal and Conjunctival Staining (lissamine green)
- Schirmer's Test
- [REDACTED]
- Monitoring and Query of AEs

- Study Drug Dispensation Prior to discharge from the study site on Visit 5 (Day 29), subjects will be educated in on self-administration of study drug. Subjects will receive two new assigned study drug kits with sufficient supply to last until Visit 6 and will be instructed to NOT self-administer study drug on the morning of their next scheduled study visit (Visit 6, Day 57 ± 3). Subjects will self-administer morning dose after visit is complete, regardless of the time, and instructed to administer an evening dose that night.

- Schedule Next Visit Subjects will be scheduled for Visit 6.

8.4.7 **Visit 6: Day 57 ± 3 –Week 8 and Study Exit**

- Study Drug Collection All used/unused study drug vials dispensed for Days 29 to 57 should be collected and reviewed by a trained study technician.
- Site staff must confirm subjects have NOT administered their morning study drug dose at home. If subject dosed prior to the visit, study visit procedures should begin 4 hours after the time of dosing.
- Monitoring and Query of AEs
- Record all Changes in Concomitant Medications
- Urine Pregnancy Test (for females of childbearing potential)
- Ora Calibra® Ocular Discomfort Scale
- Ora Calibra® Ocular Discomfort & 4-Symptom Questionnaire
- VAS
- OSDI[©]
- BCVA Utilizing an ETDRS Chart
- Slit-Lamp Biomicroscopy
- Conjunctival Redness
- TFBUT
- Corneal and Conjunctival Staining (fluorescein)
- Corneal and Conjunctival Staining (lissamine green)
- Schirmer's Test
- Intraocular Pressure
- Dilated Fundoscopy
- Blood Sampling for Immunogenicity Testing [REDACTED]
- Study Exit

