8.5 Compliance with Protocol

Subjects will be instructed on proper instillation and storage of study drug at the end of Visits 1, 2, 3, 4, and 5, and given written instructions. The subject's used and unused study drug vials will be collected at each visit from Visit 2 up to and including Visit 6 to assess dosing compliance. Dosing compliance will be based off the returned used and unused ampoule count. If the subject is less than 80% or more than 125% compliant with dosing based on the expected number of unused ampoules, then the subject will be deemed non-compliant, and a deviation should be recorded. If the subject is deemed non-compliant, the subject should be re-educated on IP compliance.

These guidelines will be used by the Investigator for determining the subject's necessary compliance for the study and for recording deviations from this compliance.

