8.8 Study Duration

An individual subject's participation will involve at least 6 visits over approximately a 10-week (~70 days) period (56 days of treatment and 14 days pre-screening).

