11.5.1 Labeling/Packaging

Run-in and Investigational drug will be packaged and labeled into clinical kits.

For the run-in period, 17 pouches will be packaged in a 2-week clinical kit. Each pouch will contain 2 single-use ampoules to provide a sufficient medication supply for one day.

For the treatment period, 17 pouches will be packaged in a 2-week clinical kit. Each subject will receive 4 kits. Each pouch will contain 2 ampoules to provide a sufficient supply of randomized study drug for one day.

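### SAP 12.1 adds missed vials to the count of doses taken, which overstates compliance, and its denominator expects two Visit 6 doses that the protocol does not schedule

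*SAP*

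**What the plan says.** SAP 12.1 defines compliance as doses taken divided by doses expected, times 100. Doses taken come from "subtracting the number of unused vials from the number of vials dispensed plus the total number of vials missed", the last item being an eCRF entry that is not defined. Doses expected are 2 × (completion or discontinuation date − Day 1 + 1), or 1 for a subject who discontinues on Day 1. Subjects are classed as under-compliant below 80% and over-compliant above 125%.

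Protocol 8.5 has no term for missed vials: "Dosing compliance will be based off the returned used and unused ampoule count". It applies the same limits with a different reference quantity: "If the subject is less than 80% or more than 125% compliant with dosing based on the expected number of unused ampoules".

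The dosing schedule comes from the visit descriptions. At Visit 2, "The initial, self-administered dose taken in-office at Visit 2 will be counted as a morning dose regardless of visit time", and an evening dose follows. At Visit 5 (protocol 8.4.6) subjects "will be instructed to NOT self-administer study drug on the morning of their next scheduled study visit", which is Visit 6. At Visit 6 (protocol 8.4.7), "All used/unused study drug vials dispensed for Days 29 to 57 should be collected", the subject exits, and no instillation or dispensing is listed. Protocol 8.8 gives "56 days of treatment and 14 days pre-screening".

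**The concern.** The sign of the last term in the numerator looks wrong. Dispensed minus unused already treats every vial not returned unused as a dose taken. A missed vial should therefore leave that figure alone (a skipped dose already among the unused) or lower it (a vial lost without being used). Adding it can only raise the count.

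The denominator appears to count the exit day as a full dosing day, although the protocol withholds the morning dose and takes back the drug at that visit. This error is small and runs the other way.

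At stake are the under- and over-compliant classes in Table 14.3.7 and the values in Listing 16.2.5.5, where a reader would look for under-dosing. With the numerator as written, the more completely a site records missed doses, the better its subjects appear to comply.

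**Working it through.** **Inputs**
- Vials dispensed: protocol 11.5.1 says "For the treatment period, 17 pouches will be packaged in a 2-week clinical kit. Each subject will receive 4 kits", with 2 ampoules per pouch, so D = 4 × 17 × 2 = 136.
- Doses scheduled for a Day 57 exit: two per day on Days 1 to 56 and none on the Visit 6 day, so 2 × 56 = 112.
- Doses expected under SAP 12.1 for a Day 57 exit: 2 × (57 − 1 + 1) = 114.
- Assumptions: one vial per dose, in-office doses drawn from the kits, no replacement kits.

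The plan gives a rule but no worked figure, so there is none to reproduce. U is vials returned unused, M is vials missed, and the SAP score is (D − U + M) / 114.

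**Numerator, missed = skipped and returned unused.** With t doses taken, U = 136 − t, so D − U + M = t + M. If every skipped dose is recorded, M = 112 − t and the numerator is always 112.

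| Taken of 112 | True | None recorded | All recorded | Reads compliant once |
|---|---|---|---|---|
| 84 | 75.0% | 84/114 = 73.7% | 112/114 = 98.2% | 8 of 28 recorded: 92/114 = 80.7% |
| 60 | 53.6% | 60/114 = 52.6% | 112/114 = 98.2% | 32 of 52 recorded: 92/114 = 80.7% |

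One fewer recorded dose gives 91/114 = 79.8% in either row.

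**Numerator, missed = lost.**
- *Lost without being used.* With 84 taken and 20 lost, U = 136 − 84 − 20 = 32. The SAP count is 136 − 32 + 20 = 124, or 124/114 = 108.8%, against a true 84/112 = 75.0%. Of the 40-dose excess, 20 come from D − U alone (104/114 = 91.2%) and 20 from the added term.
- *Used, then lost.* With all 112 taken, U = 24 and D − U = 112 is already right. If 31 empties are lost, the SAP count is 136 − 24 + 31 = 143, or 143/114 = 125.4%, which flags a fully adherent subject as over-compliant. Without the added term a Day 57 completer cannot exceed 136/114 = 119.3%.

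Doses taken are overstated by M or by 2M whenever M is above zero.

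**Denominator alone.** The excess is two doses for any Visit 6 day. A full adherer scores:
- Day 54: 106/108 = 98.1%
- Day 57: 112/114 = 98.2%
- Day 60: 118/120 = 98.3%

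With the numerator corrected, a Day 57 completer with 90 or 91 doses (90/112 = 80.4%, 91/112 = 81.25%) would score 90/114 = 78.9% or 91/114 = 79.8% and be labelled under-compliant.

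**The case against.** The eCRF is not available, so nobody can show from these documents that the field will be above zero. The author may also have meant dispensed − (unused + missed), which is right for vials lost unused: 136 − (32 + 20) = 84. That is a fair guess at intent, but it is not what is written. It would also subtract skipped doses twice if they are already among the unused: 84 taken and 28 skipped gives 136 − (52 + 28) = 56. The written formula would work only if unreturned used vials were counted as unused, and protocol 8.5 works from returned counts.

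On the denominator, the protocol synopsis also describes the treatment period as 57 ± 3 days, and SAP 12.2 counts exposure inclusively in the same way. A subject who doses before Visit 6 is allowed for by a 4-hour wait. None of this schedules a Visit 6 dose, and SAP 3.1 itself gives 56 days. It does show that the inclusive count may be a deliberate convention, and that 12.2 needs a look when 12.1 is changed. The effect is indeed small: under two percentage points for a full adherer.

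Two further objections have force. Protocol 8.5 is an operational rule for investigators, and SAP 1 says that its methods supersede the protocol's, so the statement in SAP 18 that nothing has changed is weak evidence of an undeclared departure. Also, non-compliance deviations are summarized separately (SAP 9.2) and drug accountability is listed (Listing 16.2.5.4), so under-dosing would not vanish from the report entirely. The table meant to show compliance would still be wrong.

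**Conclusion.** Both points hold. The numerator has the wrong sign under either natural meaning of a missed vial, and inflates compliance whenever that field is above zero. With complete recording of skipped doses, every Day 57 completer scores 98.2% whatever was actually taken. The denominator is two doses too large for a subject exiting at Visit 6, a relative loss of about 1.7% to 1.9% across the visit window, so it does not offset the numerator error.

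The percentages rest on a Day 57 exit and the kit assumptions above, and the numbers skipped or lost are illustrative. The wrong sign and the two-dose excess do not depend on the kit count. For early-termination exits the denominator error depends on dosing on the last day.

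The consequences are limited to Table 14.3.7 and Listing 16.2.5.5. Estimand 1 uses data regardless of compliance, so the primary result does not change. The per-protocol set could be touched only through deviations that sites record under protocol 8.5. This should be corrected, but it does not threaten the trial's main conclusion.

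**What to change.** In SAP 12.1:
- Delete the added term, so that doses taken = vials dispensed − vials returned unused.
- Define the eCRF field. Subtract further only vials recorded as lost or unreturned and not taken, never skipped doses already among the unused. Without this step the lost-vial example above would still read 104/112 = 92.9%.
- For subjects exiting at Visit 6, set expected doses to 2 × (exit date − Day 1), and keep the Day 1 exception.
- For early-termination exits, state whether exit-day doses count, and treat them alike in numerator and denominator.
- State in SAP 12.2 whether exposure remains an inclusive calendar count, so that 57 exposure days beside 56 dosing days is explained.

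Reconcile protocol 8.5 with SAP 12.1, so that both apply the 80% and 125% limits to the same ratio of doses taken to doses expected.

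The cost is a few sentences in the SAP and one clarifying phrase in the protocol. Deleting the term and changing the denominator need no new data. Subtracting lost vials is possible only if the eCRF separates them from skipped doses, which the documents do not show.
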